8.1.10. Rechallenge

8.1.10.1. Study Treatment Restart or Rechallenge

Study treatment restart or rechallenge after any stopping criteria are met by any participant in this study is not allowed for that individual.

8.2. Withdrawal from the Study

- A participant may withdraw from the study at any time at his/her own request, or may be withdrawn at any time at the discretion of the investigator for safety, behavioural, compliance or administrative reasons.
- If the participant withdraws consent for disclosure of future information, the sponsor may retain and continue to use any data collected before such a withdrawal of consent.
- If a participant withdraws from the study, he/she may request destruction of any samples taken and not tested, and the investigator must document this in the site study records.
- Refer to the SoA for data to be collected at the time of follow-up and for any further evaluations that need to be completed.

8.3. Lost to Follow Up

A participant will be considered lost to follow-up if he or she repeatedly fails to return for scheduled visits and is unable to be contacted by the study site.

The following actions must be taken if a participant fails to return to the clinic for a required study visit:

- The site must attempt to contact the participant and reschedule the missed visit as soon as possible and counsel the participant on the importance of maintaining the assigned visit schedule and ascertain whether or not the participant wishes to and/or should continue in the study.
- Before a participant is deemed lost to follow up, the investigator or designee must make every effort to regain contact with the participant (where possible, 3 telephone calls and, if necessary, a certified letter to the participant's last known mailing address or local equivalent methods). These contact attempts should be documented in the participant's medical record.

• Should the participant continue to be unreachable, he/she will be considered to have withdrawn from the study with a primary reason of lost to follow-up.

9. STUDY ASSESSMENTS AND PROCEDURES

- Study procedures and their timing are summarized in the SoA. Acceptable time windows around the nominal time points for specific assessments will be included in the SRM and assessments performed within these time windows will not constitute a protocol deviation.
- Protocol waivers or exemptions are not allowed
- Immediate safety concerns should be discussed with the sponsor immediately upon occurrence or awareness to determine if the participant should continue or discontinue study treatment.
- Adherence to the study design requirements, including those specified in the SoA, is essential and required for study conduct.
- All screening evaluations must be completed and reviewed to confirm that potential participants meet all eligibility criteria. The investigator will maintain a screening log to record details of all participants screened and to confirm eligibility or record reasons for screening failure, as applicable.
- The maximum amount of blood collected from each participant over the duration of the study, including any extra assessments that may be required, is not planned to exceed 500 mL.
- Repeat or unscheduled samples may be taken for safety reasons or for technical issues with the samples.

9.1. Efficacy Assessments

Not applicable.

9.2. Adverse Events

The definitions of an AE or SAE can be found in Appendix 4.

The investigator and any designees are responsible for detecting, documenting, and reporting events that meet the definition of an AE or SAE and remain responsible for following up AEs that are serious, considered related to the study treatment or the study, or that caused the participant to discontinue the study (see Section 8).

9.2.1. Time Period and Frequency for Collecting AE and SAE Information

• All SAEs will be collected from the start of study treatment until the follow-up visit at the time points specified in the SoA (Section 2). However, any SAEs assessed as related to study participation (e.g., study treatment, protocol-mandated procedures, invasive tests, or change in existing therapy) or related to

a GSK product will be recorded from the time a participant consents to participate in the study.

- All AEs will be collected from the start of study treatment until the follow-up visit at the time points specified in the SoA (Section 2).
- Medical occurrences that begin before the start of study treatment but after obtaining informed consent will be recorded as Medical History in the participant's source notes not the AE section of the CRF.
- All SAEs will be recorded and reported to the sponsor or designee immediately and under no circumstance should this exceed 24 hours, as indicated in Appendix 4. The investigator will submit any updated SAE data to the sponsor within 24 hours of it being available.
- Investigators are not obligated to actively seek AEs or SAEs in former study participants. However, if the investigator learns of any SAE, including a death, at any time after a participant has been discharged from the study, and he/she considers the event to be reasonably related to the study treatment or study participation, the investigator must promptly notify the sponsor.
- The method of recording, evaluating, and assessing causality of AEs and SAEs and the procedures for completing and transmitting SAE reports are provided in Appendix 4.

9.2.2. Method of Detecting AEs and SAEs

Care will be taken not to introduce bias when detecting AE and/or SAE. Open-ended and non-leading verbal questioning of the participant is the preferred method to inquire about AE occurrence.

9.2.3. Follow-up of AEs and SAEs

After the initial AE/SAE report, the investigator is required to proactively follow each participant at subsequent visits/contacts. All SAEs will be followed until the event is resolved, stabilized, otherwise explained, or the participant is lost to follow-up (as defined in Section 8.3). Further information on follow-up procedures is given in Appendix 4.

9.2.4. Regulatory Reporting Requirements for SAEs

- Prompt notification by the investigator to the sponsor of a SAE is essential so that legal obligations and ethical responsibilities towards the safety of participants and the safety of a study treatment under clinical investigation are met.
- The sponsor has a legal responsibility to notify both the local regulatory authority and other regulatory agencies about the safety of a study treatment under clinical investigation. The sponsor will comply with country-specific regulatory requirements relating to safety reporting to the regulatory authority, IRB/ IEC, and investigators.

- Investigator safety reports must be prepared for suspected unexpected serious adverse reactions (SUSAR) according to local regulatory requirements and sponsor policy and forwarded to investigators as necessary.
- An investigator who receives an investigator safety report describing a SAE or other specific safety information (eg, summary or listing of SAE) from the sponsor will review and then file it along with the IB and will notify the IRB/IEC, if appropriate according to local requirements.

9.2.5. Pregnancy

- Details of all pregnancies in female partners of male participants will be collected after the start of study treatment and until the final follow-up visit.
- If a pregnancy is reported, the investigator should inform GSK within 24 hours of learning of the pregnancy and should follow the procedures outlined in Section 12.5.
- Abnormal pregnancy outcomes (eg, spontaneous abortion, fetal death, stillbirth, congenital anomalies, ectopic pregnancy) are considered SAEs.

9.3. Treatment of Overdose

For this study, any dose of GSK3358699, LPS challenge agent, GM-CSF challenge agent or cantharidin, greater than the protocol planned doses or doses defined as part of dose escalation decisions, will be considered an overdose.

9.3.1. GSK3358699

In the event of an overdose of GSK3358699, the investigator/treating physician should:

- 1. Contact the Medical Monitor immediately.
- 2. Closely monitor the participant for AE/SAE and laboratory abnormalities until study treatment can no longer be detected systemically (at least 48 hours).
- 3. Obtain a plasma sample for PK analysis within 8 hours of the last dose of study treatment if requested by the Medical Monitor (determined on a case-by-case basis).
- 4. Document the quantity of the excess dose as well as the duration of the overdosing in the CRF.

Decisions regarding dose interruptions or modifications will be made by the investigator in consultation with the Medical Monitor based on the clinical evaluation of the participant.

GSK does not recommend specific treatment for an overdose. The Investigator (or physician in charge of the participant at the time) will use clinical judgment to treat any overdose.

9.3.2. Cantharidin

Participants will not have access to cantharidin and overdose is therefore extremely unlikely. In the event of overdose, the clinical management will be based on symptomatic

treatment and supportive measures as indicated and required according to current UK guidelines.

In case of any overexposure to Cantharone refer to the MSDS.

Inhalation: Remove victim to fresh air. Give oxygen or artificial respiration if necessary.

Skin Contact: Immediately flood affected skin with water while removing and isolating all contaminated clothing. Gently wash all affected skin areas thoroughly with soap and water. Seek medical attention if warranted.

Eye Contact: First check the victim for contact lenses and remove if present. Flush victim's eyes with water or normal saline solution for 20 to 30 minutes while simultaneously calling a hospital or poison control centre. Do not put any ointments, oils, or medication in the victim's eyes without specific instructions from a physician. Immediately transport the victim after flushing eyes to a hospital even if no symptoms (such as redness or irritation) develop.

Ingestion: Do not induce vomiting. If the victim is conscious and not convulsing, give 1 or 2 glasses of water to dilute the chemical and immediately call a hospital or poison control centre. Immediately transport the victim to a hospital. If the victim is convulsing or unconscious, do not give anything by mouth, ensure that the victim's airway is open, and lay the victim on his/her side with the head lower than the body. Transport the victim immediately to a hospital.

9.3.3. LPS

LPS dose selection has been made on the basis of a lower dose and potency than is usually reported in the literature, and thus overdose is not anticipated.

Intravenous LPS has the potential to be extremely harmful in overdose and induce symptoms and organ dysfunction in keeping with septic shock. Participants who receive an overdose of intravenous LPS will be hydrated with rapid intravenous fluid boluses. Clinical staff may need to expedite immediate transfer to hospital in the event that volunteers exhibit clinical signs of septic shock. Mild pyrexia and malaise may be observed.

9.3.4. GM-CSF

GM-CSF dose selection has been made on the basis of a lower dose than is usually reported in the literature/given to patients, and thus overdose is not anticipated.

In case of overdose, participant will be carefully monitored for white blood cell (WBC) increase and respiratory symptoms. Symptomatic management will be carried out according to existing guidelines.

9.4. Safety Assessments

Planned time points for all safety assessments are provided in the SoA.

9.4.1. Physical Examinations

- A complete physical examination will include, at a minimum, assessments of the skin, cardiovascular, respiratory, gastrointestinal and neurological systems. Height and weight will also be measured and recorded.
- A brief physical examination will include, at a minimum, assessments of the skin, lungs, cardiovascular system, and abdomen (liver and spleen).
- Investigators should pay special attention to clinical signs related to previous serious illnesses.

9.4.2. Body Weight

Body weight will be measured at the time points in the SoA. In Part A, body weight measured in treatment Period 4 Day -1 will be used to calculate the dose of LPS and GM-CSF to be used. In Part C (Cohort 4 and 8 only) body weight measured on the day prior to challenge administration will be used to calculate the dose of LPS and GM-CSF to be used.

9.4.3. Assessment of blister sites

• Visual assessment of blister site will be carried out at selected visits as detailed in the SoA.

9.4.4. Vital Signs

- Tympanic temperature, heart rate, respiratory rate, and blood pressure will be assessed.
- Vital signs measurements are to be taken before blood collection for laboratory tests.
- Tympanic temperature and respiratory rate will be taken as single measurements at the timepoints detailed in the SoA.
- Blood pressure and pulse measurements will be assessed in a semi-supine position with a completely automated device. Manual techniques will be used only if an automated device is not available.
- Blood pressure and pulse measurements should be preceded by at least 5 minutes of rest for the participant in a quiet setting, in a semi-supine position, without distractions (eg, television, cell phones).
- In Part A and Part B, blood pressure and pulse measurements will be performed as follows.
 - Day -1, Day 1 pre-dose, 24 h and 48 h post-dose: triplicate measurements
 - Day 1 post-dose: single measurements throughout except for:
 - GSK3358699 C_{max} timepoint; triplicate measurement
 - For 12 hours post-LPS challenge: triplicate measurement

- In Part C (Cohorts 4 and 8), blood pressure and pulse measurements will be performed as follows:
 - Day 1 to Day 13: triplicate measurements
 - Day 14 pre-dose, Day 15 and Day 16: triplicate measurements
 - Day 14 post-dose: single measurements throughout except for:
 - GSK3358699 approximate C_{max} timepoint; triplicate measurement
 - For 12 hours post-LPS challenge: triplicate measurement
- In Part C (Cohorts 5 7), blood pressure and pulse measurements will be performed as follows:
 - Day 1 to Day 13: triplicate measurements
 - Day 14 pre-dose, Day 15 and Day 16: triplicate measurements
 - Day 14 post-dose: single measurements throughout except for:
 - GSK3358699 approximate Cmax timepoint; triplicate measurement
- At timepoints where triplicate measurements of pulse and blood pressure are required, 3 consecutive readings will be recorded at intervals of at least 1 minute.

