2.3. Part C General Schedule of Activities Cohorts 5-7 (no challenges)

	Screening (up to 35 prior to Day 1)	Treatment Period																	Follow-up post-la	Notes
Procedure	up to 35 Days Day 1)	Day -1	Day 1	Day 2	Day 3	Day 4	Day 5	Day 6	Day 7	Day 8	Day 9	Day 10	Day 11	Day 12	Day 13	Day 14	Day 15	Day 16	Follow-up 1 (7-14 days post-last dose)	
General																				
Informed consent	Х																			
Inclusion and exclusion criteria	х	х																		Day -1 assessment is to recheck eligibility against medical conditions, prior therapy etc, but not against Day -1 clinical chemistry and haematology results (see Section 9.4.7).
Demography	Х	ļ	ļ	į	į	į	ļ	į	ļ	ļ	į	į	į	İ	İ	į	ļ	į		
Medical/medication/ drug/alcohol history	х	х																		Includes substance usage and family history of premature CV disease and current medical conditions.
Admission to unit for in-patient stay		Х																		
Discharge from Unit following in- patient stay																		x		
Outpatient visit	Х	1									1					1			Х	
Safety Assessments including	ety Assessments including laboratory tests																			
Full Physical Exam	Х																			
Brief Physical Exam		X			Ì			Ì				Ì	Ì			İ		X	Х	
Vital Signs	х	х	x	x		x				х				x	x	x	x	x	х	BP, HR, temperature, respiratory rate. See Section 2.3.1 for time points on Day 13, 14, 15 and 16. Measurements will be performed pre-dose on other dosing days.
12-Lead ECGs	x	x	x	x	x	x	x	x	x	x	x	x	x	x	x	x	x	x	x	12 Lead ECGs will be performed in triplicate at screening, Day-1, pre-dose Day 1, Day 4, Day 8, Day 14 and Day 16. Single ECGs will be performed at other time points and if any cardiac symptoms are experienced. ECGs to be performed prior to any blood draws or dosing scheduled for the same nominal time point.

	Screening (up to 35 prior to Day 1)							٦	reat	ment	Perio	bd							Follow-up post-la	Notes
Procedure	up to 35 Days Day 1)	Day -1	Day 1	Day 2	Day 3	Day 4	Day 5	Day 6	Day 7	Day 8	Day 9	Day 10	Day 11	Day 12	Day 13	Day 14	Day 15	Day 16	Follow-up 1 (7-14 days post-last dose)	
Telemetry			x			x				x						x				Continuous cardiac telemetry on each designated day from 1hr pre-dose until 24 h post-dose, and on other days if QTcF >450msec.
Holter monitoring (24 hours)	Х																			If a participant is rescreened the Holter will not need to be repeated.
HIV, Hep B, Hep C	Х	1	İ	İ	İ	1	İ	İ	Ì	Ì	1	1			1	1	İ	İ		

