Blood sampling for intracellular PK [S3]			x			x				х				x		x	х	х		On Day 1 samples will be taken at 1h, 4h and 8h post-dose. Pre- dose samples Days 4, 8 and 12. See Section 2.3.1 for Day 14, 15 and 16 sample timings.
Blood sample for ex vivo PD assay [S4]		x	x	x		x				x				x		x	x	x		Day -1 samples to be taken at approximately 13:00, 17:00 and 20:00. Day 1 and Day 14 pre-dose samples to be taken at approximately 08:00. Day 1 post-dose samples to be taken at 1h, 4h and 8h post-dose. Samples to be taken pre-dose Days 2, 4, 8 and 12. See Section 2.3.1 for Day 14, 15 and 16 sample timings. All sample timepoints pre- and post-dose require 1 LPS and 1 LPS + GSK3358699 sample.
Blood sample for circulating proteins [E1a]			x	х		x				х				x		x	х			On Day 1 samples will be taken at pre-dose, 2h, 4h and 8h post- dose. Samples to be taken pre-dose Day 2, 4, 8 and 12. See Section 2.3.1 for Day 14 and 15 sample timings.
Blood sample for gene panel [E1b]			x			x				х				х		x	х			On Day 1 samples will be taken at pre-dose, 2h and 4h post- dose. Samples to be taken pre-dose Days 4, 8 and 12. See Section 2.3.1 for Day 14 and 15 sample timings.
Blood sample for cellular activation markers [E2b]			Х			Х				Х				Х		Х				Pre-dose samples Days 1, 4, 8 and 12. See Section 2.3.1 for Day 14 sample timings.
Blood sample for potential companion diagnostic development		x																		
Blood sample for CES genotyping and optional genetic research [E5]		х																		
Urine sample for metabolite analysis [E4]			x	х												x	х			A 0-24 urine collection will be made on Day 1 and Day 14. In each case, for the pre-dose sample, immediately prior to dosing participants will be instructed to void their bladder into a collection container. Following dosing participants will be instructed to collect all urine voided for a 0-24 hour collection.

2.3.1. Part C Day 14 Detailed SoA for PK and PD / Biomarker Sampling Cohorts 5-7 (no challenges)

Procedure	Day 13		1	1	1	Day	/ 14.	1	1	1	1	Day 15	Day 16	
	13	Pre-dose	0 h	15 mins	30 mins	1 h	2 h	4 h	6h	4 8 h	12 h	24 h	48 h	Notes
Treatment / agent administra	tion and	PK sa	mpling											
Study Drug / Placebo Administration			х											
Vital Signs	Х	Х								Х		Х	Х	
Haematology	Х									Х		Х	Х	
Coagulation										Х				
Blood sampling for systemic PK [S1] and [S2]		Х		Х	Х	Х	Х	Х	Х	Х	Х	Х	Х	Ad-hoc sample to be taken in the event of any cardiac arrhythmias, as close as possible to the time of occurrence

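### Cohorts 5-7: the Day 14 schedule has no slot for the vital-sign reading near Cmax that Section 9.4.4 requires, and on-treatment ECGs have no stated post-dose hour

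*Protocol*

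**What the plan says.** Section 4 of the Protocol lists vital signs and 12-lead ECGs as endpoints of the primary safety objective.

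**Vital signs.** Section 9.4.4 has a rule written for Cohorts 5-7. Blood pressure and pulse are triplicate on Days 1-13, before the Day 14 dose, and on Days 15 and 16. After the Day 14 dose they are single, with one exception: "GSK3358699 approximate C_{max} timepoint; triplicate measurement". The vital-signs note in Section 2.3 directs the site as follows: "See Section 2.3.1 for time points on Day 13, 14, 15 and 16. Measurements will be performed pre-dose on other dosing days". Section 2.3.1 then marks vital signs on Day 13 (no hour), on Day 14 at pre-dose and 8 h, and at 24 h and 48 h. SAP Section 13.1.2.1 reproduces the same marks.

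**ECGs.** Section 2.3 marks a 12-lead ECG on every day from Day -1 to Day 16. Its note reads "12 Lead ECGs will be performed in triplicate at screening, Day-1, pre-dose Day 1, Day 4, Day 8, Day 14 and Day 16" and continues "Single ECGs will be performed at other time points and if any cardiac symptoms are experienced". Section 2.3.1 has no ECG row, and Section 9.4.5 refers back to the schedule for times.

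**Telemetry.** Section 2.3 has continuous telemetry on Days 1, 4, 8 and 14, from 1 h before dosing to 24 h after it.

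**Parts A and B.** Sections 2.1 and 2.2 schedule both vital signs and ECGs at 2, 4, 8 and 12 h after dosing.

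**Analysis.** SAP Section 13.2.1 bases summaries on nominal visits. SAP Section 13.4.2 keeps unscheduled visits out of summary tables and figures and puts them in listings only.

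**The concern.** The body of the Protocol asks for a reading that its schedule does not contain. Section 9.4 says that the planned times of all safety assessments are found in the schedule, so a site working from the tables has no slot that prompts the Cmax reading. If staff take it anyway because they have read 9.4.4, it has no nominal time. If it is then recorded as unscheduled, it drops out of the SAP's Part C vital-sign tables (2.43 and 2.44).

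The ECG gap is of a different kind. No passage contradicts another, but nothing requires any on-treatment 12-lead ECG to fall near peak exposure. QTc prolongation is a named risk in Section 3.3.1, QTcF is a withdrawal criterion in Section 8.1.2, and the dose escalation committee reviews individual ECGs and vital signs before the next repeat-dose level (Section 5.1.3.2). What these data can say about repeat dosing depends on when they were taken relative to dose.

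**Working it through.** The plan states no figure to reproduce: Section 10.1 sets no formal hypothesis and Section 10.2.1 bases the sample size on feasibility. The check is a comparison of the schedule with the text, plus one timing calculation.

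**1. Day 14 vital signs.**

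| Source | Day 14 times |
|---|---|
| Section 9.4.4, Cohorts 5-7 | pre-dose; single readings post-dose; triplicate at approximate Cmax |
| Section 2.3.1 | pre-dose, 8 h (then 24 h and 48 h) |
| SAP Section 13.1.2.1 | pre-dose, 8 h (then 24 h and 48 h) |
| Section 2.1.1, expected Cmax | 0.5-2 h |

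The vital-signs row is empty in every column from 15 min to 6 h. Two separately printed copies agree, so this is not a damaged table. No slot falls in the 0.5-2 h window.

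**2. Other dosing days.** Vital signs are marked on Days 1, 2, 4, 8 and 12, and the note makes these pre-dose. Day 13 is sent to Section 2.3.1, which gives no hour. The number of vital-sign slots with a stated hour within 6 h after any of the 14 doses is therefore 0. Section 9.4.4 names the Cmax reading for Day 14 only, so Days 1-13 show a gap and not a contradiction.

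**3. ECGs.** The only dose-related time in the note is pre-dose. The number of ECGs with a stated post-dose hour on a dosing day is 0. The ECGs on Days 15 and 16 follow the last dose by about 24 and 48 h.

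**4. Plasma level at the scheduled times.** Inputs are tmax 0.5-2 h (Section 2.1.1) and a predicted systemic half-life of about 3 h (Section 5.4). One-phase decline is an assumption made here, as is the half-life range of 2-4 h used to test it.

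Share of peak at time t = 2^(-(t - tmax)/half-life).

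- 8 h, half-life 3 h: 2^(-7.5/3) = 0.18 for tmax 0.5 h; 2^(-6/3) = 0.25 for tmax 2 h.
- 8 h, widest range: 2^(-7.5/2) = 0.07 (half-life 2 h, tmax 0.5 h) to 2^(-6/4) = 0.35 (half-life 4 h, tmax 2 h).
- 24 h (next pre-dose), half-life 3 h: 2^(-23.5/3) = 0.004 to 2^(-22/3) = 0.006; widest range 0.0003 to 0.022.
- 2 h (the first slot in Parts A and B), half-life 3 h: 2^(-1.5/3) = 0.71 to 1.00; widest range 0.59 to 1.00.

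**The case against.** **Section 9.4.4 is itself binding, and timing can be changed.** The notes that close Section 2 let the team alter assessment times without an amendment, and give getting closer to peak plasma concentration as an example. This stands to the extent that the peak *can* be missed, not that it *must* be. It makes correction easy but does not remove the conflict.

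**The sponsor chose lighter monitoring for these cohorts.** The Amendment 4 table says so, because there is no challenge to monitor. Yet the Cohorts 5-7 part of 9.4.4 keeps the Cmax reading explicitly.

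**Telemetry covers the peak.** For rhythm and heart rate on Days 1, 4, 8 and 14 this stands. Telemetry supplies neither blood pressure nor the 12-lead QTcF used in SAP Tables 2.38-2.40. SAP Section 8.3 names telemetry, but the display list has only Holter tables, and Holter recording is at screening only.

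**Part A already measured the peak.** Section 7.2 keeps Part C doses within those of Part A, and the SAP shows that Part A included 10 mg, the dose given in Part C. With so little parent drug left at 24 h, plasma accumulation should be small. This lowers the stakes for a plasma-driven effect, but it is single-dose evidence.

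**Plasma Cmax may be the wrong marker.** The active acid is retained in target cells (Section 3), and Section 3.3.1 reports no correlation between systemic concentration and the NSVT cases. So peak effect need not follow plasma parent drug, and the arrhythmias alone do not argue for a Cmax reading. This limits what step 4 means; it does not explain why a required reading has no slot.

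**A reader might infer that all on-treatment ECGs are at trough.** The documents do not support that. The list containing the word pre-dose ends with Day 16, when no dose is given, so the word cannot govern the whole list and most naturally belongs to Day 1. One mark per day does not mean one ECG: Day 1 systemic PK is also one mark but ten samples. The ECG hours are unspecified, not shown to be pre-dose.

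**Conclusion.** For Cohorts 5-7 the schedule and Section 9.4.4 contradict each other on Day 14: a required triplicate blood pressure and pulse reading has no slot, and the SAP carries the omission over. The first post-dose vital-sign slot, at 8 h, is at about 18-25% of peak plasma parent drug, or 7-35% over half-lives of 2-4 h. Those percentages rest on one-phase decline, a tmax of 0.5-2 h and a half-life predicted before any human data. They describe plasma parent drug, not effect.

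The ECG part is an omission: the plan does not ensure an on-treatment QTcF near peak exposure. It would be tempting to conclude that the Part C QTcF tables reflect only low concentrations. That does not follow, because no ECG hour is stated and the 8 h figure belongs to a vital-sign slot. Nor can one say that no vital signs are taken soon after any repeat dose, since the Day 13 hour is open.

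This should be corrected because it affects two primary safety endpoints at almost no cost. Its practical reach is limited: SAP Section 2.3 says that, of these cohorts, only Cohort 5 was dosed, and Section 13.6.1 says that it was terminated early.

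**What to change.** Reconcile Sections 2.3 and 2.3.1, and the SAP copy in 13.1.2.1, with Section 9.4.4, so that the approximate-Cmax vital-sign reading already required appears as a nominal Day 14 time point and enters the SAP summaries. Give Day 13 vital signs an hour. Add an ECG row to 2.3.1 with Day 14 times stated relative to dose, without displacing the Day 14 triplicate already scheduled.

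For Cohort 5 data already collected, report for every participant the actual time from dose of each on-treatment vital-sign and ECG reading, and state in the study report how many fell near the expected Cmax. The planned Part C listings of ECG values and vital signs (59, 60, 63 and 64) are restricted to values of potential clinical importance or to participants who have one, so they would not show this for everyone.

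The cost is a documented schedule correction, which the Section 2 notes allow without an amendment, one extra summary of times, and a few minutes of staff time on a PK profiling day. No visit is added.
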